### **Dose escalation for augmenting treatment responses**

The AG-221 dose for the subsequent treatment cycles that are given may be increased from 100 mg QD to 200 mg QD if the following occurs:

- ANC  $< 0.5 \times 10^9/L$  after being on AG-221 for the first cycle without  $\geq$  Grade 3 AEs suspected by the investigator to be related to AG-221; or
- no partial remission (PR) achieved after being on AG-221 for at least 2 cycles without  $\geq$  Grade 3 AEs suspected by the investigator to be related to AG-221; or
- evidence of morphologic relapse or PD

If benefit is demonstrated with an increased level of dose, then that dose level should be maintained during the subsequent treatment cycles that are given. However, once increased, the AG-221 dose may be reduced if a certain level of toxicity (eg, Section 7.2.1.3) is observed and considered as possibly or probably related to AG-221 treatment. A maximum of 3 steps of AG-221 dose reduction, stepwise first from 200 mg QD to 150 mg QD, second from 150 mg QD to 100 mg QD, and then last from 100 mg QD to 50 mg QD, are permitted in the event of toxicities, depending on the dose that the subject is on. Once reduced, the AG-221 dose should not be re-escalated unless there is evidence of morphologic relapse or PD. Any subject who is unable to tolerate 50 mg QD of AG-221 should be discontinued from study treatment.

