11.1. Adverse Events

Adverse events will be analyzed in terms of treatment-emergent adverse events (TEAEs) which are defined as any AEs that begin or worsen on or after the start of study drug through 28 days after the last study treatment or until the EOT visit, whichever is longer, as well as those serious adverse events (SAEs) made known to the Investigator at any time thereafter that are suspected of being related to investigational product. All AEs will be coded using the Medical Dictionary for Regulatory Affairs® (MedDRA) version 22.0. The severity will be graded by the study personnel based on NCI National Cancer Institute Common Terminology Criteria for Adverse Events (CTCAE) Version 4.03.

A treatment-related TEAE is defined as TEAE that is suspected by the Investigator to be related to study treatment.

If a subject experiences the same AE more than once with different toxicity grade, then the event with the highest grade will be tabulated in “by grade” tables. If a subject experiences multiple AEs under the same preferred term (system organ class), then the subject will be counted only once for that preferred term (system organ class).

Summarizations of TEAEs per person-year of exposure are carried out in exposure-adjusted event rate, which is defined as number of events occurred in treatment exposure duration.

The number of subjects with at least one TEAE will be summarized. The incidence of TEAEs will be summarized by alphabetic order of SOC and descending order of PT for AG-221 group. Tables summarizing the incidence of TEAEs will be generated for each of the following:

- Summary of TEAEs;
- All TEAEs by SOC and PT;
- All TEAEs by decreasing frequency of PT for AG-221;
- All TEAEs per person-year of exposure, person-years of exposure is defined as (Sum of subjects’ overall treatment exposure (days) from first dose date (or randomization date for BSC only group) to the end of the TEAE period [c])/365.25;
- TEAEs related to study treatment;
- TEAEs by maximum severity;

- TEAEs with CTCAE grade ≥ 3 ;
- Related TEAEs with CTCAE grade ≥ 3 ;
- TEAEs with CTCAE grade ≥ 3 per person-years exposure;
- Related TEAEs with CTCAE grade ≥ 3 per person-years exposure;
- All AEs resulting in death;
- Serious TEAEs;
- Serious TEAEs per person-years exposure;
- All serious TEAEs by decreasing frequency of PT for AG-221;
- Serious TEAEs related to study treatment;
- Serious TEAEs related to study treatment per person-years exposure;

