- TEAEs leading to study drug withdrawal;
- TEAEs leading to study drug withdrawal per person-years exposure;
- TEAEs related to study drug and leading to study drug withdrawn;
- TEAEs with leading to dose reduction;
- TEAEs with leading to dose reduction per person-years exposure;
- TEAEs related to study drug and leading to study drug dose reduction;
- TEAEs leading to study drug dose interruption;
- TEAEs leading to study drug dose interruption per person-years exposure;
- TEAEs related to study drug and leading to study drug dose interruption;
- TEAEs leading to study drug dose reduction and dose interruption;
- TEAEs related to study drug and leading to dose reduction and study drug dose interruption;
- TEAEs for the following baseline subgroups (provided when the number of subjects is sufficient):
 - Gender (male and female);
 - Age (≥ 60 years and < 70 years, ≥ 70 years and < 80 years, ≥ 80 years);
 - Region (North America, South America, Europe, Australia, Asia; US vs. Non-US);
 - Baseline ECOG performance status (Grade 0, 1, 2);
 - Prior intensive therapy for AML (yes versus no) (IVRS and CRF source);
 - Primary refractory: yes versus no
 - Prior allogeneic HSCT for AML (yes versus no) (IVRS and CRF source);

- Baseline ANC value ($\leq 0.5 \times 10^9/L$, $0.5 < 1 \times 10^9/L$, $\geq 1 \times 10^9/L$)
- Baseline creatinine clearance value (< 45 , $45 < 60$, ≥ 60 mL/min);
- Best clinical response (CR, PR, SD, PD) adjusted by person years on treatment.

In addition, the impact of dose escalation to AEs will be explored. Sensitivity analyses will be carried out for the following two tables:

- All TEAEs by AG-221 ≤ 100 mg and AG-221 > 100 mg cohorts:
AEs which occurred in subjects which only received doses of AG-221 ≤ 100 mg, and AEs which occurred prior to a dose switching to > 100 mg for subjects which had an escalated dose, or AEs which occurred following a reduction to ≤ 100 mg following an escalation are to be counted in ≤ 100 mg cohort. Only AEs which occurred after a dose > 100 mg was administered and occurred within 28 days following this dose administration, and where there were no subsequent dose reductions between escalated dose date and AE start date will be counted in the > 100 mg cohort.
- TEAEs with CTCAE grade ≥ 3 by AG-221 ≤ 100 mg and AG-221 > 100 mg cohorts.

Listings for the corresponding summary tables will be presented separately. Non-treatment-emergent AEs will also be included in one of the listings.

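### The two adverse-event tables by AG-221 dose cohort compare unequal time at risk with no denominator or exposure adjustment, so crude incidence could make doses above 100 mg look safer or worse whatever the true effect.

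*SAP*

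**What the plan says.** SAP 11.1 introduces its main list of adverse-event tables with "Tables summarizing the incidence of TEAEs will be generated for each of the following", and counts a subject once per preferred term. Where exposure adjustment is intended, the SAP names it: "Summarizations of TEAEs per person-year of exposure are carried out in exposure-adjusted event rate". Tables of that kind carry the label in their titles, for example "TEAEs with CTCAE grade ≥ 3 per person-years exposure". Person-years for the all-TEAE table are built from each subject's "overall treatment exposure (days) from first dose date", which is not divided by dose. SAP 9.1 summarizes duration of exposure by treatment group.

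After that list come two further tables, described as sensitivity analyses: all TEAEs, and TEAEs of Grade 3 or higher, each by AG-221 dose cohort (at most 100 mg, or more than 100 mg). Their stated purpose is: "In addition, the impact of dose escalation to AEs will be explored". The attribution rule is asymmetric:

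- **At most 100 mg:** all events in subjects who never exceeded 100 mg, plus events before escalation and events after a reduction to 100 mg or less.
- **More than 100 mg:** only events that followed an escalated dose and "occurred within 28 days following this dose administration, and where there were no subsequent dose reductions between escalated dose date and AE start date".

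Neither table has a person-year label or a stated denominator.

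Under Protocol 7.2.1 every subject in the AG-221 arm starts at 100 mg. Protocol 7.2.1.2 then allows escalation by three routes: low ANC after the first cycle, or "no partial remission (PR) achieved after being on AG-221 for at least 2 cycles without" a related event of Grade 3 or worse (a condition that the ANC route shares), or relapse or progressive disease.

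**The concern.** A once-per-subject incidence rises with time observed. Here the lower-dose cohort holds the whole treatment course of never-escalated subjects and the early course of everyone else. The higher-dose cohort holds only a later segment in some subjects. Every escalated subject who was treated as planned contributes to both. A difference between the two columns could therefore reflect how long each cohort was watched and not the dose.

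These are the only adverse-event comparisons by dose level in the SAP, and the protocol permits escalation to 200 mg, so readers will use them to judge how the higher dose is tolerated. The all-TEAE and Grade 3 or higher tables by treatment arm have person-year versions. The same two tables by dose cohort, where time at risk is less comparable, do not.

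**Working it through.** The plan gives no figure to reproduce. The check asks whether crude incidence under the stated rule can recover a known dose effect.

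**Inputs from the documents.** Cycle length is 28 days (Protocol 6.2), the planned AG-221 arm is 158 (SAP 4.4), and the attribution rule is in SAP 11.1.

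**Assumptions, because the documents do not give them.** Event risk p per cycle is 10% (range 5% to 20%), with a constant rate. Cycles at risk are 1 to 6 at the lower dose and 1 to 4 at the higher. For the mixed example, 30% of the arm escalates.

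**Formula.** With rate ratio r at the higher dose and c cycles at risk, crude incidence = 1 − (1 − p)^(r × c).

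**Results at p = 10%**

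| Cycles, ≤100 mg | Cycles, >100 mg | True r | Crude, ≤100 mg | Crude, >100 mg |
|---|---|---|---|---|
| 6 | 2 | 1 | 1 − 0.9^6 = 46.9% | 1 − 0.9^2 = 19.0% |
| 2 | 4 | 1 | 1 − 0.9^2 = 19.0% | 1 − 0.9^4 = 34.4% |
| 6 | 2 | 2 | 46.9% | 1 − 0.9^4 = 34.4% |
| 4 | 2 | 2 | 34.4% | 34.4% |

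The first two rows have no dose effect, yet one suggests protection and the other harm. In the third row a true doubling looks like benefit, and in the fourth it disappears. The columns are equal when r equals the ratio of cycles at risk, so with 6 versus 2 cycles the rate would have to triple (6/2 = 3) before they matched.

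**Range of p, no dose effect.** At 5%, 6 versus 2 cycles gives 26.5% versus 9.8%, and 2 versus 4 cycles gives 9.8% versus 18.5%. At 20% the figures are 73.8% versus 36.0%, and 36.0% versus 59.0%. The pattern does not change.

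**Mixed arm.** Take 158 subjects, 47 escalated after 2 cycles and then followed for 2 more, and 111 never escalated with 6 cycles.

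- Lower-dose person-time: (111 × 6 + 47 × 2) × 28/365.25 = 58.3 person-years.
- Higher-dose person-time: 47 × 2 × 28/365.25 = 7.2 person-years.
- Lower-dose crude incidence: (111 × 46.9% + 47 × 19.0%)/158 = 38.6%.
- Higher-dose crude incidence over the 47: 19.0% with no effect, 34.4% with a doubling.
- If all 158 were the denominator, the doubling would show as 47 × 34.4%/158 = 10.2%. The unstated denominator therefore matters as much as the unstated time.

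**Rates by dose state.** The assumed rate is −ln(0.9) × 365.25/28 = 1.37 per person-year. Dividing events by person-time in each dose state gives 1.37 versus 1.37 with no effect and 1.37 versus 2.75 with a doubling, for any split of cycles. This holds because the rate is assumed constant.

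**The case against.** The SAP never says that these two tables are crude. It says only which events count in which cohort. That is correct, so crude incidence is an inference. It rests on the section's incidence default, the missing person-year label and the absence of any dose-level person-time. Read most generously, the measure is unspecified, and the remedy is the same.

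The 28-day limit is not in itself an unusual truncation. The general TEAE window also runs to 28 days after last treatment, or to the EOT visit if longer. With daily dosing, the limit can be read as rolling forward from each escalated dose. That objection stands, but it does not equalize the cohorts: the lower-dose cohort still holds all the time of never-escalated subjects. If the limit instead runs from the first escalated dose, the higher-dose window shrinks to one cycle.

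A reader might go further in four ways that the documents do not support:

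- *The SAP exposure-adjusts nearly all its other adverse-event tables.* It does not. In the main list, 8 of the 27 entries before the subgroup item are per person-year.
- *This is the only look at the safety of escalation.* SAP 9.6 also summarizes escalated subjects, dose modifications after escalation and the reasons for them.
- *Escalated subjects are mostly free of related Grade 3 or worse events.* Only two of the three routes carry that condition, and the share using each is not given.
- *The higher dose will look safer.* The second row of the table shows the opposite, and the relapse or progression route could add disease-related events at the higher dose.

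Finally, person-year rates do not remove selection into escalation or the effect of time since treatment start. That stands, and the fix has to say so.

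**Conclusion.** The point holds in limited form. If the rule is followed as written with incidence as the measure, the comparison depends on time at risk and cannot separate a dose effect from length of observation. Under the assumed 10% risk per cycle, the gap with no dose effect runs from 27.9 points in favor of the higher dose (46.9% − 19.0%, 6 versus 2 cycles) to 15.4 points against it (34.4% − 19.0%, 2 versus 4 cycles). These sizes are illustrations. Neither the size nor the direction in the trial can be stated, because the documents give no split of time by dose, share escalated or event rate.

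A reader might infer that exposure adjustment would turn these tables into a fair test of dose toxicity. It would not. It removes the dependence on length of observation under a constant rate and leaves the selection and timing problems in place. The analysis is exploratory, and OS, the key secondary endpoints and Type I error are unaffected. This is a desirable improvement, not a necessary one.

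**What to change.** For both dose-cohort tables:

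1. Split each AG-221 subject's on-treatment time at the escalation and reduction dates, so that every day and every event belongs to one dose state. This also settles where time at 150 mg after a step down from 200 mg belongs, which the current wording leaves open.
2. State the number of subjects and the person-years in each dose state.
3. Report events per person-year, with the same carry-over rule for the events and for the person-time, and say whether the 28 days run from the first or from any escalated dose.
4. Add a footnote that rates by dose state do not remove selection into escalation (Protocol 7.2.1.2) or the effect of time since treatment start.

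The cost is a little more programming. Protocol 7.6 already has dosing and dose changes recorded in the eCRF, and SAP 11.1 already uses exposure-adjusted event rates. The tables stay exploratory.

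### SAP 11.1: the two AG-221 dose-cohort rules are not complementary, so on the plain wording AEs starting on 150 mg after a 200-to-150 mg reduction enter neither exploratory table column

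*SAP*

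**What the plan says.** SAP 11.1 introduces two AG-221 tables with "In addition, the impact of dose escalation to AEs will be explored" and calls them sensitivity analyses. One covers all TEAEs, the other TEAEs of grade 3 or higher. Each is split into a ≤100 mg and a >100 mg cohort.

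Three kinds of event go to the ≤100 mg cohort:
- "AEs which occurred in subjects which only received doses of AG-221 ≤ 100 mg";
- "AEs which occurred prior to a dose switching to > 100 mg for subjects which had an escalated dose";
- "AEs which occurred following a reduction to ≤ 100 mg following an escalation are to be counted in ≤ 100 mg cohort".

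The >100 mg cohort is defined exclusively: "Only AEs which occurred after a dose > 100 mg was administered and occurred within 28 days following this dose administration", with the further condition "where there were no subsequent dose reductions between escalated dose date and AE start date will be counted in the > 100 mg cohort". There is no third or default cohort.

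Protocol 7.2.1.2 raises the dose in one step from 100 mg to 200 mg. Reductions for toxicity run "stepwise first from 200 mg QD to 150 mg QD, second from 150 mg QD to 100 mg QD", and last to 50 mg. Protocol 7.1.1 lists 150 mg among the supplied tablet strengths.

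**The concern.** The lower-cohort rule tests whether the reduction reached 100 mg or less. The upper-cohort rule tests whether there was any reduction at all. These are not opposites, and 150 mg lies between them: it is above 100 mg, yet in the protocol's sequence it is normally reached by a reduction.

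The tables exist to show what escalation does to AEs, and the label >100 mg covers 150 mg. The events at risk of omission belong to subjects who have already been reduced from 200 mg, and they include any toxicity on 150 mg that leads to the next step down. Time on 150 mg need not be short, because Protocol 7.2.1.2 restricts re-escalation after a reduction to relapse or progression.

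There is also a mismatch with efficacy. The dose-group analyses in SAP 10.2, 10.3.1.1 and 10.3.1.2 treat anyone with at least one dose above 100 mg as escalated. A subject's survival and response would then count as >100 mg while that subject's AEs on 150 mg would not.

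**Working it through.** The plan states no figure to reproduce. The check is to apply the rules to the protocol's dose sequence.

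**Trace for an AE starting on 150 mg after 200 → 150 mg**

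1. Lower cohort, first limb: the subject has received more than 100 mg. Fails.
2. Lower cohort, second limb: the AE is not before the switch above 100 mg. Fails.
3. Lower cohort, third limb: there was a reduction, but to 150 mg. Fails.
4. Upper cohort, timing: dosing above 100 mg continues, so the AE is within 28 days of such a dose, provided the window runs from the latest one. Passes on that basis.
5. Upper cohort, no reduction since the *escalated dose date*: the step to 150 mg intervened. Fails.

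Result: neither cohort.

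**Sensitivity to the undefined term**

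The SAP does not define *escalated dose date*. Three readings were applied to nine dose paths. In the escalated paths, 200 mg starts on Day 57 and, where reduced, 150 mg starts on Day 85.

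- Reading A: the escalated dose date is the step-up date, and the 28 days run from the latest dose >100 mg.
- Reading A28: both run from the step-up dose.
- Reading B: both refer to the latest dose >100 mg, even if that is 150 mg.

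| AE onset | A | A28 | B |
|---|---|---|---|
| On 100 mg, never escalated | ≤100 | ≤100 | ≤100 |
| On 100 mg, before escalation | ≤100 | ≤100 | ≤100 |
| On 200 mg, Day 67 (67 − 57 = 10 days after step-up) | >100 | >100 | >100 |
| On 200 mg, Day 117 (117 − 57 = 60 days after step-up) | >100 | neither | >100 |
| On 150 mg, Day 100 (100 − 85 = 15 days after reduction) | neither | neither | >100 |
| On 150 mg, Day 128 (128 − 85 = 43 days after reduction) | neither | neither | >100 |
| On 100 mg after 200 → 150 → 100 | ≤100 | ≤100 | ≤100 |
| On 150 mg, re-escalated from 100 mg | >100 | >100 | >100 |
| On 50 mg after all steps down | ≤100 | ≤100 | ≤100 |

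No path falls in two cohorts. Unclassified paths number two under A, three under A28 and none under B. Reading A28 also loses AEs on 200 mg itself after 28 days, so the window needs an explicit starting point.

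**Late-onset events**

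SAP 11.1 defines TEAEs as running to 28 days after last treatment or to the EOT visit, whichever is longer, plus later related SAEs. An event starting more than 28 days after a last dose of 150 or 200 mg therefore also has no cohort.

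**The case against.** The strongest reply is reading B. A 150 mg administration is a dose above 100 mg, the 28-day window makes most sense if it runs from each such dose, and SAP 11.1 elsewhere uses an escalated dose as shorthand for anything above 100 mg. If the escalated dose date is that same administration, every tested path has exactly one cohort. This reading is possible, but the SAP does not state it, and calling a dose reached by reduction an escalated dose is strained. Two programmers could produce different tables.

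Other objections stand and limit the point:

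- A reader might infer that toxicity above 100 mg is left out generally. It is not. AEs on 200 mg before the reduction still count, including the one that triggers it (given a window from the latest dose).
- A reader might infer that these AEs vanish from the safety report. They stay in the main TEAE, serious and grade ≥3 tables and in the listings. AEs leading to dose reduction have their own table, and SAP 9.6 summarises modifications after escalation.
- SAP 11.1 counts a subject once per preferred term. A recurrence on 150 mg of a term already counted on 200 mg changes no incidence figure; new terms, or a rise to grade ≥3, could.
- A reader might expect the two columns to sum to the AG-221 total. Subject counts need not, because one subject can appear in both cohorts.

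**Conclusion.** The point holds as a classification gap in two exploratory tables. On the plain wording, AEs with onset on 150 mg after the 200-to-150 mg step enter neither cohort, and this omission can only lower event counts in the >100 mg column. The conclusion rests on reading the escalated dose date as the step-up date and, for the second table, on the same rule carrying over from the first.

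The number of AEs lost cannot be estimated from the documents. Purely as illustration, assume that 20–40% of 158 AG-221 subjects escalate (158 × 0.20 ≈ 32; 158 × 0.40 ≈ 63) and that 25–50% of those step down to 150 mg (32 × 0.25 = 8; 63 × 0.50 ≈ 32). That gives 8 to 32 subjects. A reader might take this as the size of the bias, but the rates are assumed, and the result counts subjects exposed to the gap, not lost events. The gap does not depend on it.

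No primary, key secondary or main safety analysis is affected. The point concerns the analysis rule only and says nothing about which dose is appropriate.

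**What to change.** In SAP 11.1:

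1. Replace the no-reduction condition of the >100 mg rule with: *no subsequent reduction to ≤ 100 mg before the AE start date*. This gives it the same threshold as the third limb of the ≤100 mg rule.
2. State that the 28 days run from the most recent dose above 100 mg, whether 150 or 200 mg.
3. Assign TEAEs starting more than 28 days after the last dose by the last dose received, or show them separately. Do not default them to ≤100 mg: that would move late events in subjects who stopped on 150 or 200 mg into the low-dose column.
4. State that the same rule applies to the grade ≥3 table.
5. Make any reconciliation against all AG-221 TEAEs at event level, with late-onset events accounted for.

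The cost is a few lines of SAP text and a small programming change before database lock for the final analysis. No additional data are needed and there is no effect on subjects.

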11.2. Adverse Events of Special Interest

The following TEAEs of special interest will be summarized:

1. QT prolongation;
Standardized MedDRA Query (SMQ) Torsade de pointes/QT prolongation.
2. IDH inhibitor associated Differentiation syndrome (IDH-DS);
 - a. TEAE AE differentiation syndrome as reported by the investigators.
 - b. Time to IDH-DS: Summary statistics including mean, standard deviation, median, minimum, maximum will be provided.
 - i. From start of treatment until an event of IDH-DS
 - ii. From onset until end date of an event of IDH-DS
 - c. Signs and symptoms of PT IDH-DS (% of subject with specific symptom with denominator of N of subjects with completed CRF page for the differentiation syndrome).
 - Symptoms of the IDH-DS (from the CRF AE page)
 - Treatment for IDH-DS: systemic steroids
 - Mean duration of steroid treatment for the IDH-DS
 - Study drug interruption, discontinuation, dose adjustment due to IDH-DS
 - d. Concurrency of the IDH-DS and tumor lysis syndrome PT.
3. Bilirubinemia and liver safety;
 - a. SMQ Biliary system related investigations, signs and symptoms (narrow terms)
 - b. SMQ Drug related hepatic disorders (broad terms).
 - c. Time to onset and time to resolution
4. Hepatic Disorders;
5. Acute Renal Failure;
6. Pulmonary Events;
7. Peripheral Neuropathy
8. Hepatobiliary Disorders;

The following summaries will be provided for TEAEs of special interest:

- All TEAEs by PT;
- Treatment related TEAEs by PT;
- Serious TEAEs by PT;
- Serious treatment related TEAEs by PT;
- TEAEs with CTCAE grade of Grade ≥ 3 ;

- Treatment related TEAEs with CTCAE grade of Grade ≥ 3 ;
- Time to first onset of TEAE;

